### 2.3 Study Design

Randomization will be stratified by age (age 18-29, 30-40) and presence of fibroids. The randomization scheme will be coordinated through the data coordination center (DCC).

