## **2.7 Statistical Analysis**

Since the number of patients for this study is minimal and multiple factors are of concern, descriptive statistics will be used, and the study is expected to be under powered to perform any formal statistical inference. The number, mean, standard deviation, median, interquartile range of the level of the pharmacokinetic parameters of EGCG and 2 of the major metabolites at different time points and the difference from screening to Visit 1, Visit 2 or Visit 4, and the changes in liver function, estrogen levels, endometrial thickness, and follicular measurements will be presented for the three treatment groups, and then stratified by age group and/or the presence or absence of uterine fibroid. For comparison, a two-way ANOVA will be used to compare the effects of the three treatments and the presence of fibroids on the above outcome parameters. With a sample size of 36 patients for the three treatment groups, which includes 18 subjects with uterine fibroids and 18 without uterine fibroids, with an alpha of 0.05, the power of the study would be 0.44 and 0.85 for a medium (0.25) or large (0.4) effect size, respectively. There are insufficient preliminary data

in the literature to support or not support the reasonableness of these effect sizes. For the comparison of serum folate levels among wildtype MTHFR, MTHFR (C677T), and MTHFR (A1298C) patients, ANOVA (unadjusted) and multivariate linear regression will be used.

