#### 4.3.2 Study Population

Thirty-six (36) patients will be equally randomized via computer-generated randomization schedule to receive:

1. Two capsules of decaffeinated Green Tea extract (close to 800mg EGCG) taken orally on a daily basis for up to 2 months
2. Two capsules of decaffeinated Green Tea extract taken orally on a daily basis for up to 2 months with clomiphene citrate 100mg for 5 days
3. Two capsules of decaffeinated Green Tea extract taken orally on a daily basis for up to 2 months with letrozole 5mg for 5 days.

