## 5.5 Randomization/Treatment Initiation

Thirty-six (36) patients will be equally randomized via computer-generated randomization schedule to receive: 1) 800 mg of decaffeinated EGCG taken orally on a daily basis with food for up to 2 months; 2) 800 mg of decaffeinated EGCG taken orally on a daily basis with food for up to 2 months with clomiphene citrate 100mg for 5 days; 3) 800 mg of decaffeinated EGCG taken orally on a daily basis with food for up to 2 months with letrozole 5mg for 5 days.

Treatment assignments will be randomized for age groups and presence of fibroids by a varying-block-size design. The DCC statisticians will generate the randomization scheme for the study.

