### 6.4 Difference in serum folate levels among wildtype MTHFR, MTHFR (C677T), and MTHFR (A1298C) patients. Statistical Analyses

Since the number of patients for this study is minimal and multiple factors are of concern, descriptive statistics will be used, and the study is expected to be under powered to perform any formal statistical inference. The number, mean, standard deviation, median, interquartile range of the level of the pharmacokinetic parameters of EGCG and 2 of the major metabolites at different time points and the difference from screening to Visit 1 or Visit 2 or Visit 4, and the changes in liver function, hormone levels, endometrial thickness and follicular measurements will be presented for the three treatment groups, and then stratified by age group and/or the presence or absence of uterine fibroid. Patients with a detectable EGCG level at the screening visit will be excluded. For comparison, a two-way ANOVA will be used to compare the effects of the three treatments and the presence of fibroids on the above outcome parameters. With a sample size of 36 patients for the three treatment groups, and 18 subjects with uterine fibroids and 18 without uterine fibroids, with an alpha of 0.05, the power of the study would be 0.44 and 0.85 for a medium (0.25) or large (0.4) effect size, respectively. There are insufficient preliminary data in the literature to support or not support the reasonableness of these effect sizes. For the comparison of serum folate levels among wildtype MTHFR, MTHFR (C677T), and MTHFR (A1298C) patients, ANOVA (unadjusted) and multivariate linear regression will be used.

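### Age group is a randomisation stratum but is missing from the two-way ANOVA; adding it is a modest, nearly free gain in precision if age predicts outcome

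*Combined protocol and SAP*

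**What the plan says.** Section 2.3 sets the design: "Randomization will be stratified by age (age 18-29, 30-40) and presence of fibroids". Sections 4.3.1 and 5.1 repeat it, and section 5.5 gives the method: "Treatment assignments will be randomized for age groups and presence of fibroids by a varying-block-size design".

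The only model for comparing the three arms is in section 2.7, repeated in section 6.4: "a two-way ANOVA will be used to compare the effects of the three treatments and the presence of fibroids". The outcomes covered are the pharmacokinetic parameters and the changes in liver function, estrogen or hormone levels, endometrial thickness and follicular measurements.

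Age appears in the analysis only where the summaries are first shown by arm and "then stratified by age group and/or the presence or absence of uterine fibroid", so even the descriptive split by age is optional. A regression is planned for folate by MTHFR genotype, but its covariates are not named and it is not the arm comparison.

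Both sections also say that descriptive statistics will be used and that formal inference is expected to be underpowered. They still specify the ANOVA, set its level ("with an alpha of 0.05") and give power figures.

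**The concern.** One of the two stratification factors is in the model and the other is not, and no reason is given. Stratifying on age makes the arms alike in age, so most of the age-related variance drops out of the true variance of an arm difference. An ANOVA without age does not know this and counts that variance as residual error. Its standard errors then overstate the real uncertainty, and its F test rejects less often than the nominal level.

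What is at stake is precision. With 36 women there is little to spare, and the sponsor itself thought age important enough to stratify on.

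**Working it through.** **Inputs from the documents.** Section 2.7: "With a sample size of 36 patients for the three treatment groups, which includes 18 subjects with uterine fibroids and 18 without uterine fibroids". Section 4.3.2: "Thirty-six (36) patients will be equally randomized via computer-generated randomization schedule to receive" one of three regimens. That gives 12 women per arm and 6 per arm-by-fibroid cell. A 3 x 2 ANOVA with interaction has 36 - 6 = 30 error degrees of freedom, or 29 with age added. The plan does not say whether the interaction is fitted; the additive version is shown below.

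**Inputs assumed.** R2 is the share of variance within arm-by-fibroid cells that is due to age group. The documents give no value, so the range 0 to 0.30 is shown. Perfect balance means 36/12 = 3 women per arm x fibroid x age cell.

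**The plan's own power figures.** Section 2.7 states power of 0.44 and 0.85 at effect sizes f of 0.25 and 0.4. From the noncentral F distribution with noncentrality 36 x f^2 and 2 and 30 degrees of freedom, the treatment test has power 0.229 and 0.521. The stated figures are not reproduced at 36 women; 72 women (2 and 66 degrees of freedom) give 0.443 and 0.853. That is a separate matter. It matters here only because the power figures below start from 0.23 and 0.52.

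**Standard error under perfect balance.** Set the within-cell variance to 1. Code age as +a and -a in equal halves, with a^2 = R2. The variance left after age is 1 - R2, and this governs the true standard error of an arm difference. Without age in the model, the age sum of squares, 36 x R2, falls into the residual:

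- expected residual mean square = [30(1 - R2) + 36 R2]/30 = 1 + 0.2 R2
- reported SE / true SE = sqrt[(1 + 0.2 R2)/(1 - R2)]

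At R2 = 0.20 this is sqrt(1.04/0.80) = 1.140. In the additive model (32 error degrees of freedom) the numerator is 1 + 0.125 R2, giving sqrt(1.025/0.80) = 1.132, so the choice matters little.

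**Simulation under perfect balance** (40,000 trials per setting, 3 x 2 model with interaction; f is scaled to the within-cell SD before age is removed):

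| R2 | SE ratio, formula | SE ratio, simulated | Type I error, without -> with age | Power at f = 0.25, without -> with age | Power at f = 0.4, without -> with age |
|---|---|---|---|---|---|
| 0 | 1.000 | 1.004 | 0.050 -> 0.050 | 0.23 -> 0.23 | 0.52 -> 0.52 |
| 0.05 | 1.031 | 1.033 | 0.043 -> 0.050 | 0.21 -> 0.24 | 0.51 -> 0.54 |
| 0.10 | 1.065 | 1.067 | 0.035 -> 0.049 | 0.20 -> 0.25 | 0.51 -> 0.57 |
| 0.20 | 1.140 | 1.146 | 0.022 -> 0.050 | 0.17 -> 0.28 | 0.48 -> 0.62 |
| 0.30 | 1.231 | 1.230 | 0.012 -> 0.050 | 0.15 -> 0.31 | 0.46 -> 0.68 |

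**Approximate balance.** Only the fibroid split is fixed by the plan. Age counts will vary, and blocks may be incomplete in each of the four strata. Simulating random age counts with blocks of 3 or 6 (assumed), and age splits of 50/50, 70/30, or 40% older without fibroids and 80% older with (also assumed), the reported SE exceeds the true SE by about 0%, 2%, 3-5%, 10% and 14-19% at the same five values of R2.

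**Cost when age is irrelevant.** At R2 = 0 the error degrees of freedom go from 30 to 29, and calculated power goes from 0.229 to 0.228 and from 0.521 to 0.520.

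**The case against.** The strongest reply is that the size rests on an unsupported range. The documents link age group to no outcome and give no SD. For two equal age groups, R2 corresponds to a gap of 2 x sqrt[R2/(1 - R2)] within-group SDs: 0.46 at R2 = 0.05, 0.67 at 0.10, 1.0 at 0.20 and 1.31 at 0.30. The plan's own large effect, f = 0.4, is a gap of 0.8 SD for two equal groups. The upper two values therefore make age group a stronger influence than the effect the plan calls large. This stands, and the lower end of the range deserves more weight.

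Second, several outcomes are changes from screening. Subtraction removes any stable difference in level between age groups, so R2 for a change may be well below R2 for a level. This also stands.

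Third, the plan lists means, SDs, medians and interquartile ranges, promises no confidence intervals, and disclaims formal inference. This limits the consequence but does not remove the point. An ANOVA at a stated alpha is still planned, and its residual error should match the design.

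A reader might go further and infer that the benefit of stratifying by age is lost, that the arm comparison is biased, or that false positives become more likely. None of these follows. Stratification still balances age between arms and lowers the true variance of the contrast; only the model's own estimate of error misses that gain. The error runs in the conservative direction.

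**Conclusion.** The mismatch is in the text and the direction of its effect is clear. Leaving age out makes the ANOVA's standard errors and tests conservative whenever age group predicts the outcome, and has no effect when it does not. Under realistic, imperfect balance the excess in the standard error is about 2% to 5% for R2 of 0.05 to 0.10, reaching 14-19% only if age explains 30% of the variance. These sizes depend on the assumed R2, block sizes and age split.

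The documents do not support reading this as a flaw that threatens the trial's conclusions. It is a small avoidable loss of precision in a study that describes itself as descriptive, and a cheap one to avoid.

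**What to change.** In the ANOVA of sections 2.7 and 6.4, add age stratum (18-29, 30-40) as a main effect alongside treatment and fibroids, for the pharmacokinetic and secondary arm comparisons. Use the stratum as recorded at randomisation, and state whether the treatment-by-fibroid interaction is fitted. No new data, visits or change to the randomisation are needed. The cost is one model term and one error degree of freedom.

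### The stated power (0.44 and 0.85) does not follow from 36 women; the planned two-way ANOVA gives 0.23 and 0.52 for treatment, and the stated pair matches 72 women

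*Combined protocol and SAP*

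**What the plan says.** Section 2.7 bases the power figure on a total of 36 women in three arms, half of them with fibroids and half without, tested at a significance level of 0.05. The test is a two-way ANOVA with treatment and presence of fibroids as factors. The result is that "the power of the study would be 0.44 and 0.85 for a medium (0.25) or large (0.4) effect size, respectively". Section 6.4 repeats the claim on the same basis: "With a sample size of 36 patients for the three treatment groups, and 18 subjects with uterine fibroids and 18 without uterine fibroids".

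Section 4.3.2 sets the allocation: "Thirty-six (36) patients will be equally randomized via computer-generated randomization schedule to receive" one of three regimens. Sections 2.5 and 6.2 make the difference between the three groups in pharmacokinetic parameters the primary outcome.

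Sections 2.7 and 6.4 also say that the analysis is descriptive and that "the study is expected to be under powered to perform any formal statistical inference". They add that there are too few preliminary data to judge whether the effect sizes are reasonable. The documents contain no other power or sample-size calculation. They do not name the effect-size index, and they do not say whether the power refers to treatment, fibroids or the interaction term.

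**The concern.** Power of 0.85 for a large effect looks too high for a three-group comparison with 12 women per arm. It also sits awkwardly with the statement, in the same paragraph, that the study cannot support formal inference.

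The figure affects how a null result is read. Sections 3.1 and 5.2 say that the pharmacokinetics and hepatic safety of EGCG with clomiphene citrate or letrozole are unknown, and that the results will be used to confirm hepatic safety for the larger FRIEND study. The ANOVA covers the pharmacokinetic parameters and the changes in liver function. A reader who relies on 0.85 would think that a non-significant treatment difference leaves only a 15% chance of having missed a large effect.

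**Working it through.** **Inputs**

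| Input | Value | Source |
|---|---|---|
| Total N | 36 | 2.7, 6.4 |
| Fibroid factor | 18 with, 18 without | 2.7, 6.4 |
| Allocation | equal over 3 arms | 4.3.2, 5.5 |
| Alpha | 0.05 | 2.7, 6.4 |
| Effect size | 0.25 and 0.4 | 2.7, 6.4 |
| Test | two-way ANOVA, 3 × 2 | 2.7, 6.4 |

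Equal allocation gives 36/3 = 12 women per arm. If each fibroid stratum is also split evenly, there are 36/6 = 6 per cell. One assumption is needed: 0.25 and 0.4 are read as Cohen's f, because the plan labels them medium and large and these are the conventional medium and large values of f in ANOVA.

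**Formula**

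Power = P(F′ > F_crit), where F′ is noncentral F with the degrees of freedom of the term and noncentrality λ = N × f². The error degrees of freedom in the full 3 × 2 model are N − 6.

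**Step 1: try to reproduce the plan's figures at N = 36**

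- λ for f = 0.25: 36 × 0.0625 = 2.25
- λ for f = 0.4: 36 × 0.16 = 5.76
- Error df: 36 − 6 = 30

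| Term (N = 36) | df | Power, f = 0.25 | Power, f = 0.4 |
|---|---|---|---|
| Treatment, or treatment × fibroids | 2, 30 | 0.229 | 0.521 |
| Treatment, no interaction term in model | 2, 32 | 0.230 | 0.524 |
| Treatment, one-way | 2, 33 | 0.231 | 0.525 |
| Fibroids | 1, 30 | 0.306 | 0.642 |
| All six cells | 5, 30 | 0.150 | 0.350 |
| **Stated in the plan** | not given | **0.44** | **0.85** |

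No row reproduces the stated pair. A simulation of the treatment test (40,000 runs per setting) gave 0.231 and 0.519, in line with the first row.

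**Step 2: other readings at N = 36**

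- Treatment test at alpha 0.10: 0.344 and 0.654. At alpha 0.20: 0.500 and 0.787.
- One-sided test for fibroids: 0.430 and 0.758. The first is close to 0.44; the second is far from 0.85.
- 0.25 and 0.4 read as f² (treatment): 0.725 and 0.908.

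None gives both figures.

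**Step 3: which N gives the stated pair?**

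At N = 72, λ = 72 × 0.0625 = 4.5 and 72 × 0.16 = 11.52, with df (2, 66). Power is 0.443 and 0.853, which round to 0.44 and 0.85; simulation gave 0.445 and 0.852. For the 2-df test, both figures match to two decimals only at N = 71 and 72, and only 72 is a balanced 3 × 2 design (12 per cell, 24 per arm). For the fibroid test and the six-cell test, no N matches both to two decimals.

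**Step 4: what 36 women can detect**

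- Chance of missing a large treatment effect: 1 − 0.52 = 0.48, against 1 − 0.85 = 0.15 as stated.
- Treatment effect detectable with 80% power: f = 0.54. With 85% power: f = 0.58.
- N for 80% power on treatment, in multiples of six: 66 for f = 0.4 and 162 for f = 0.25.

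**The case against.** The strongest defence is that the figure carries little weight in this plan. Both sections open by calling the analysis descriptive and the study underpowered, and both admit that the effect sizes lack support. Nothing says that 36 was derived from this power, or that a non-significant ANOVA will be read as no interaction or will decide whether the larger trial goes ahead. The explicit liver rules in section 4.3.6 rest on individual laboratory limits and a count of cases, not on the ANOVA. All of this stands, and it limits the practical harm. It does not make 0.85 correct. The correct value, 0.52, also agrees better with the plan's own caveat.

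The second defence is that the plan does not fully specify the calculation, and a more efficient analysis could reach the stated power with 36 women. This is true arithmetically. A between-group test averaging four time points with correlation 0.3 gives 0.441 and 0.851, and adjustment for a baseline value with correlation 0.72 gives 0.435 and 0.844. But the documents state no such correlation and describe neither analysis in connection with the power; they name a plain two-way ANOVA. What stands is that the cause of the discrepancy is not documented, so the mix-up of per-arm and per-cell numbers is only the likeliest explanation.

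**Conclusion.** The concern holds. From the plan's own inputs, power for the treatment comparison is 0.23 at f = 0.25 and 0.52 at f = 0.4, not 0.44 and 0.85. The stated figures are too high by 0.21 and 0.33 (0.44 − 0.23 and 0.85 − 0.52). The figure also fails for fibroids and for the treatment-by-fibroid term, so the conclusion does not depend on which term was meant.

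It rests on reading the effect sizes as Cohen's f, on a balanced design with 36 evaluable women, and on the ANOVA as named. The documents state no dropout allowance; any loss of women would lower the power further. That 72 women reproduce the stated pair is established by calculation. That 12 per arm was taken as 12 per cell is an inference, and the conclusion does not need it.

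**What to change.** Replace the power sentence in sections 2.7 and 6.4 with text along these lines:

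> With 36 women (12 per arm; 18 with and 18 without fibroids), alpha 0.05 and a two-way ANOVA, power for Cohen's f of 0.25 and 0.4 is 0.23 and 0.52 for treatment and for the treatment-by-fibroid term, and 0.31 and 0.64 for presence of fibroids. The treatment effect detectable with 80% power is f = 0.54. A non-significant difference between treatments will not be interpreted as absence of a drug interaction between EGCG and clomiphene citrate or letrozole.

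The wording keeps the ANOVA term apart from a pharmacological interaction, since both could be called an interaction. If the sponsor intended a repeated-measures or baseline-adjusted analysis, the plan should instead name that analysis and state the assumed correlation and its basis.

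The cost is a change of wording in two paragraphs and a less favourable power figure. No patients, visits or procedures are added.

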## 2 Study Synopsis

### 2.1 Objectives

The objective of this study is to conduct a randomized clinical trial to determine the pharmacokinetics and hepatic safety of epigallocatechin gallate (EGCG).

MTHFR represents the most studied enzyme in the folate pathway with strong evidence that polymorphisms decrease enzyme activity. Because of the potential effect of EGCG on folate metabolism possibly leading to folate depletion, MTHFR represents a clinically relevant target. We are planning to stratify subjects by wild type MTHFR, MTHFR (C677T), and MTHFR (A1298C). The prevalence of MTHFR mutations can range from 30 to 40% in the American population for C677T and ~50% for A1298C. We will evaluate if green tea catechins may have modulating properties that may increase the risk of folic acid depletion in women expressing known MTHFR polymorphisms. In this protocol we will evaluate if polymorphisms related to folate metabolism increase the risk for folate depletion in women receiving green tea extract.

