## **2.6 Secondary Outcome Parameters**

The secondary outcome parameters will include:

- Changes in liver function between the 3 groups.
- Changes in estrogen levels (E2) between the 3 groups.
- Changes in endometrial thickness and ovarian characteristics between the 3 groups.
- Change in the pharmacokinetic parameters of EGCG and metabolites within each group.
- Difference in serum folate levels among wildtype MTHFR, MTHFR (C677T), and MTHFR (A1298C) patients.

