### 6.3 Secondary Outcome Measurements

The secondary outcome parameters will include:

- Changes in liver function between the 3 groups.
- Changes in estrogen levels (E2) between the 3 groups.
- Changes in endometrial thickness and ovarian characteristics between the 3 groups.
- Change in the pharmacokinetic parameters of EGCG and metabolites within each group.

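### The folate objective asks about depletion on EGCG, but the planned unadjusted comparison of folate levels names no visit, makes no stated use of screening folate, and uses genotype labels that overlap

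*Combined protocol and SAP*

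**What the plan says.** The synopsis objective (section 2.1) is that "we will evaluate if polymorphisms related to folate metabolism increase the risk for folate depletion in women receiving green tea extract". The matching secondary outcome in 2.6 is "Difference in serum folate levels among wildtype MTHFR, MTHFR (C677T), and MTHFR (A1298C) patients". Sections 2.7 and 6.4 give the method in the same words: for the "comparison of serum folate levels among wildtype MTHFR, MTHFR (C677T), and MTHFR (A1298C) patients, ANOVA (unadjusted) and multivariate linear regression will be used". Neither names a visit, a baseline or a covariate.

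Other outcomes are handled as differences from screening or as changes. Section 2.7 says that "the changes in liver function, estrogen levels, endometrial thickness, and follicular measurements will be presented for the three treatment groups"; folate is not in that list.

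Screening folate is collected. Sections 2.4 and 4.3.3 list folate among the screening tests, before EGCG is started, and again at Visit 4. Section 6.4 adds: "Patients with a detectable EGCG level at the screening visit will be excluded". A pre-EGCG value therefore exists for each woman.

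All three arms receive EGCG. Randomisation is stratified by age and fibroids (2.3, 4.3.1, 5.1), not by genotype. On genotype frequency, 2.1 says: "The prevalence of MTHFR mutations can range from 30 to 40% in the American population for C677T and ~50% for A1298C". It does not say whether these are carrier or allele frequencies, and no section says how a woman with both variants is classified.

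Section 2.7 also limits what the study claims: "descriptive statistics will be used, and the study is expected to be under powered to perform any formal statistical inference".

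**The concern.** Depletion while taking EGCG is most naturally a question about change from the pre-EGCG value. The outcome and the only method spelled out concern levels. Section 2.1 itself says that the variants reduce enzyme activity, so on the protocol's own reasoning folate could differ by genotype before the first capsule. Such a difference would persist at Visit 4, and an unadjusted ANOVA would show it whether or not EGCG did anything.

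The second gap is the grouping. Wildtype, C677T and A1298C are treated as three groups, but one woman can carry both variants. She could be dropped, put in either variant group, or made a fourth group. The result depends on that choice, which could be made after the data are seen.

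At stake is how a secondary finding is read: a constitutional folate difference could be reported as susceptibility to EGCG.

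**Working it through.** The plan gives no figure for the folate analysis. The power values in 2.7 belong to the treatment-by-fibroid ANOVA and are not used here.

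**Inputs.** From the documents: N = 36, alpha 0.05, C677T 30–40%, A1298C about 50%. Assumed, because the documents are silent: size of the pre-EGCG shift (0.2 to 1.0 SD), screening to Visit 4 correlation ρ (0.3 to 0.7), normal data, equal SDs at the two visits.

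**1. Women with both variants.** Reading the rates as independent carrier rates:
- C677T 30%: wildtype 36 × 0.70 × 0.50 = 12.6; C677T only 36 × 0.30 × 0.50 = 5.4; A1298C only 12.6; both 5.4.
- C677T 40%: 10.8, 7.2, 10.8, 7.2.
- Without independence, both lies between 36 × max(0, p + 0.5 − 1) = 0 and 36 × 0.40 = 14.4.
- If the rates are allele frequencies (Hardy-Weinberg assumed), carrier rates are 1 − 0.7² = 0.51 or 1 − 0.6² = 0.64, and 1 − 0.5² = 0.75. Under independence, both is 36 × 0.51 × 0.75 = 13.8 or 36 × 0.64 × 0.75 = 17.3.

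Steps 2 to 5 use the carrier reading, rounded to 13/5/13/5 and 11/7/11/7.

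**2. Unadjusted level ANOVA.** Drop double carriers, assume no EGCG effect, and let one variant group be lower by d SD at both visits. With n women in total and n_k in the shifted group, the noncentrality is λ = d² × n_k(n − n_k)/n, with 2 and n − 3 degrees of freedom.
- 13/5/13, d = 0.5: λ = 0.25 × 5 × 26/31 = 1.05 (C677T only shifted), rejection 12.8%; λ = 0.25 × 13 × 18/31 = 1.89 (A1298C only shifted), rejection 19.7%.
- 11/7/11, d = 0.5: λ = 0.25 × 7 × 22/29 = 1.33, rejection 14.9%; λ = 0.25 × 11 × 18/29 = 1.71, rejection 18.0%.

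**3. Using the screening value.** Under the same shift at both visits, the shift cancels in the change score. Adjusting Visit 4 for screening leaves a residual of about d(1 − ρ); at d = 0.5 and ρ = 0.5 that is 0.25 SD. Simulated rejection rates, with the level ANOVA from step 2:

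| Shift at both visits | Level ANOVA | Change from screening | Visit 4 adjusted for screening, ρ 0.3–0.7 |
|---|---|---|---|
| 0.2 SD | 6–7% | about 5% | 5–6% |
| 0.3 SD | 8–10% | about 5% | 5–7% |
| 0.5 SD | 13–20% | about 5% | 6–12% |
| 0.8 SD | 27–45% | about 5% | 8–22% |
| 1.0 SD | 39–64% | about 5% | 9–31% |

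The 5% for change follows from the equal additive shift. If instead every woman lost the same fraction q of her folate, a group lower by d at screening would lose q × d less, and change would differ by genotype.

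**4. Effect of the label.** Keep all 36 women and lower every C677T carrier by d at both visits. With double carriers labelled A1298C, the level ANOVA rejects in 11–12% (0.5 SD) and 21–24% (0.8 SD). Labelled C677T, it rejects in 20–22% and 44–51%. The label alone roughly doubles the rate.

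**5. Precision of a two-term model.** Standard error of the C677T effect, in SDs of the outcome analysed:
- Separate carrier terms, all 36 women: √[18/(2 × 13 × 5)] = 0.37 and √[18/(2 × 11 × 7)] = 0.34; with arm and fibroid status added, 0.36–0.39.
- Double carriers dropped: √(1/5 + 1/13) = 0.53 and √(1/7 + 1/11) = 0.48.
- Interaction of the two variants: 0.68–0.74, so 36 women cannot test additivity.

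The SD of change is √[2(1 − ρ)] level SDs: 1.18, 1.00 and 0.77 at ρ = 0.3, 0.5 and 0.7. With t(33) = 2.03 and no further covariates, the 95% half-width for C677T on change is 0.82–0.90, 0.70–0.76 and 0.54–0.59 level SDs.

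**The case against.** The strongest reply is that the outcome in 2.6 is a difference in levels. If one genotype truly has lower folate, rejection is a correct answer to that outcome, and depletion could also mean low folate while on EGCG. This stands in part: a reader might infer that the ANOVA gives a false result, and the documents do not support that. What they support is that the specified comparison cannot answer the question in 2.1 as a question about EGCG.

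Second, the plan pairs the unadjusted ANOVA with a multivariable regression. A reader might infer that screening folate will be ignored altogether. The documents do not support that either, since the regression may include it. But no covariate is listed, and step 3 shows that adjustment alone leaves part of a baseline genotype difference in place. Adding screening folate to the regression would therefore reduce the problem without removing it.

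Third, nothing in the documents locates the baseline shift, its SD or the correlation. This stands in full. The rates above are an illustration, and at 0.2–0.3 SD the distortion is small. The 5% for change is likewise a product of the equal-shift assumption.

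Fourth, the study calls itself descriptive, folate is absent from the section 4 aims, and no decision depends on it. That lowers the weight, but even a descriptive table needs a visit, a baseline and defined groups.

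**Conclusion.** The point holds at low severity. As written, the folate analysis compares levels across genotype groups that were not randomised, in women who all take EGCG, without naming the visit or saying that the screening value is used. It cannot separate a difference present before EGCG from one arising on it. The three labels overlap for about 5–7 of 36 women under independent carrier rates (0 to about 14 without independence, more if the rates are allele frequencies), and no rule places these women.

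If a constant genotype shift exists, EGCG has no effect and double carriers are dropped, the level ANOVA rejects in 6–10% at 0.2–0.3 SD, 13–20% at 0.5 SD and 39–64% at 1.0 SD. Whether any such shift exists in these women is not in the documents, so a reader should not infer that a spurious finding is likely. Nor would a better model make the result confirmatory: the intervals in step 5 are wide, and with no EGCG-free arm no version of this analysis estimates an effect of EGCG.

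**What to change.** In 2.6, 2.7, 6.3 and 6.4:
- Make change in serum folate from screening to Visit 4 the main folate analysis. Fit a linear model with one term for C677T carriage and one for A1298C carriage (reference: wildtype at both sites), with treatment arm and fibroid status as covariates.
- Report Visit 4 folate adjusted for screening folate as a sensitivity analysis, noting that it does not fully remove a baseline genotype difference.
- Keep any unadjusted level comparison descriptive, shown at both screening and Visit 4.
- Summarise four groups: wildtype, C677T only, A1298C only, both.
- Give estimates with 95% confidence intervals. State that the model assumes additive effects and that, without an EGCG-free arm, the result is not an effect of EGCG.

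Two points of consistency. The list in 6.3 ends with "Change in the pharmacokinetic parameters of EGCG and metabolites within each group" and omits folate, which 2.6 includes and the heading and text of 6.4 cover; add it to 6.3. Section 4.3.3 lists folate at Visits 1 and 2, whereas 2.4 does not; reconcile them.

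The cost is wording only, because screening folate, Visit 4 folate and genotype are already collected. There are two downsides: change is noisier than a single level if the screening to Visit 4 correlation is below 0.5, and a woman missing either value drops out of the main analysis.
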